#### Data within an Individual Profile

A value within an individual profile may be excluded from analysis if any of the following criteria are met:

- For PK profiles during single dosing of non-endogenous compounds, the concentration in a pre-dose sample is quantifiable.
- For any questionable datum that does not satisfy the above criteria, the profile will be evaluated and results reported with and without the suspected datum.

#### Data between Individual Profiles

1. If  $n < 6$ , then the dataset is too small to conduct a reliable range test. Data will be analyzed with and without the atypical value, and both sets of results will be reported.
2. If  $n \geq 6$ , then an objective outlier test will be used to compare the atypical value to other values included in that calculation:
  - a. Transform all values in the calculation to the logarithmic domain.
  - b. Find the most extreme value from the arithmetic mean of the log transformed values and exclude that value from the dataset.
  - c. Calculate the lower and upper bounds of the range defined by the arithmetic mean  $\pm 3 \times \text{SD}$  of the remaining log-transformed values.
  - d. If the extreme value is within the range of arithmetic mean  $\pm 3 \times \text{SD}$ , then it is not an outlier and will be retained in the dataset.
  - e. If the extreme value is outside the range of arithmetic mean  $\pm 3 \times \text{SD}$ , then it is an outlier and will be excluded from analysis.

If the remaining dataset contains another atypical datum suspected to be an outlier and  $n \geq 6$  following the exclusion, then repeat step 2 above. This evaluation may be repeated as many times as necessary, excluding only one suspected outlier in each iteration, until all data remaining in the dataset fall within the range of arithmetic mean  $\pm 3 \times \text{SD}$  of the log-transformed values.

#### Reporting of Excluded Values

Individual values excluded as outliers will be documented in the final report. Approval of the final report will connote approval of the exclusion.

### 9.3.2 Pharmacokinetic Statistical Methodology

The galcanezumab AUC(0-∞), AUC(0-tlast), and Cmax will be log transformed and analyzed using an analysis of variance (ANOVA) model. The model will include fixed effects for injection device (PFS [reference] or AI [test]), investigative site, and injection site. The least squares means for the PFS and AI and the 90% CI for the difference in means will be estimated from the ANOVA model and back transformed from the log scale to provide estimates of the geometric means and 90% CIs for the ratio of the geometric means.

Example SAS code:

```
proc mixed data=pk;
  class device invsite injsite;
  model log_pk = device invsite injsite / cl residual;
  lsmeans device / alpha=0.1 cl pdiff;
  ods output lsmeans=lsmeans;
  ods output diffs=diffs;
run;
```

The tmax of galcanezumab between the PFS (reference) and AI (test) will be analyzed using a Wilcoxon rank-sum test. An estimate of the median difference and 90% CI will be calculated. Insert stats methodology here.

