- d Unless otherwise specified, safety monitoring procedures throughout the study should be performed at approximately the same time of day (± 2 hours) as dosing was performed on Day 1 (except for procedures scheduled at screening and Day -1).
- e Each subject will receive a single dose of 240 mg LY2951742 in the morning, administered as 2×1 -mL (120 mg/mL) subcutaneous injections of solution formulation in either a manual prefilled syringe or an autoinjector device. Injection-site reactions after injection will be assessed as part of AE collection.
- f Complete physical examination to be performed at screening and at the final visit for each subject; directed physical examination only at other visits and as clinically indicated.
- g Height to be measured at screening only.
- h Vital signs include sitting blood pressure and pulse rate.
- i Additional urine drug screen and ethanol tests may be performed at the investigator's discretion.
- j Required for females of child-bearing potential only; however, pregnancy tests carried out in females of non-childbearing potential pending receipt of follicle-stimulating hormone results will not be considered a protocol deviation. Serum pregnancy test will be done on screening, and may be repeated using urine or serum test prior to admission to the clinical research unit and as clinically indicated.
- k When possible, PK samples on follow-up outpatient visit days should be collected at a time of day close to when dosing occurred on Day 1 (± 2 hours). PK sampling times are given as targets to be achieved within reasonable limits. The actual time of PK sampling should be recorded.
- l Baseline plasma CGRP sample will be taken on Day 1 prior to study drug injection.

3. Introduction

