5.4. Scientific Rationale for Study Design

This study is open label because the primary objective for this study is to compare the relative bioavailability of LY2951742 solution as a manual PFS versus autoinjector. Pharmacokinetics is an objective endpoint; therefore, blinding is unnecessary. In addition, the overtly different appearance and operation of the test and reference injection devices (PFS and autoinjector) precludes blinding of subjects or investigators.

LY2951742 is a humanized monoclonal antibody with observed $t_{1/2}$ of approximately 3 to 4 weeks. The planned follow-up period will be 20 weeks after dosing, which enables adequate collection of PK data to assess the relative bioavailability of LY2951742 solution given by a PFS or autoinjector. The $t_{1/2}$ of LY2951742 and the required duration for the wash-out period preclude the use of a cross-over design for this study.

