10.1. Sample Size Determination

Up to 160 subjects will be enrolled (80 in each arm). The number of subjects was determined on the basis of Study I5Q-MC-CGAO Part B interim data, a Phase 1 single-dose study evaluating 300 mg LY2951742 solution administered as a PFS. The percent coefficient of variation for LY2951742 C_{max} and $AUC(0-\infty)$ was approximately 35%. One-hundred sixty (160) subjects (80 per arm) will provide approximately 90% power to demonstrate that the 90% confidence interval (CI) of the ratio of geometric means between test and reference devices for the PK parameter falls within 0.8 to 1.25, assuming the true ratio is 0.95 and 12.5% of subjects will not contribute to the endpoint.

Randomized and dosed subjects with insufficient collection of PK samples may be replaced at the discretion of the sponsor.

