10.3.2.2. Pharmacokinetic Statistical Inference

The $AUC(0-\infty)$, $AUC(0-t_{last})$, and C_{max} will be log transformed and analyzed using an analysis of variance (ANOVA) model. The model will include fixed effects for injection device (PFS [reference] or autoinjector [test]), investigative site, and injection site. The least squares means for the PFS and autoinjector and the 90% CI for the difference in means will be estimated from the ANOVA model and back transformed from the log scale to provide estimates of the geometric means and 90% CIs for the ratio of the geometric means.

The t_{max} of LY2951742 between the PFS (reference) and autoinjector (test) will be analyzed using a Wilcoxon rank-sum test. An estimate of the median difference and 90% CI will be calculated.

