## 9.2 Demographics and Subject Disposition

Subject disposition will be listed. The demographic variables age, sex, race, ethnicity, site ID, body weight, height, body mass index and smoking status will be summarized and listed. All other demographic variables will be listed.

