### **11. CHANGES FROM THE PROTOCOL SPECIFIED STATISTICAL ANALYSES**

There were no changes from the protocol specified statistical analyses.

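### The PK models leave out Day 1 predose body weight, which is already collected; the planned analysis is valid and adequately powered, but may give up precision

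*SAP*

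**What the plan says.** The protocol and the SAP agree on the PK model. Protocol 10.3.2.2 states: "The model will include fixed effects for injection device (PFS [reference] or autoinjector [test]), investigative site, and injection site". SAP 9.3.2 repeats this: "The model will include fixed effects for injection device (PFS [reference] or AI [test]), investigative site, and injection site". Its example code has the same three terms: "model log_pk = device invsite injsite / cl residual". Neither document contains a weight-adjusted PK analysis, either primary or supportive.

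The Schedule of Activities (Protocol section 2) has one row for height and weight, with entries at screening, Day 1 predose and Day 141. Footnote g says "Height to be measured at screening only", so the Day 1 predose entry is a weight. The only stated use of weight is descriptive. SAP 9.2 says "The demographic variables age, sex, race, ethnicity, site ID, body weight, height, body mass index and smoking status will be summarized and listed", and Protocol 10.2.2 plans a similar summary by device.

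Every subject receives the same 240 mg dose (Protocol 7.2.1). BMI may run from 19.0 to 35.0 kg/m² (Protocol 6.1), which at a given height allows a 35/19 = 1.8-fold range of weight. Randomization covers device and injection site, not weight (Protocol 7.2).

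**The concern.** Protocol 5.4 explains that the half-life and "the required duration for the wash-out period preclude the use of a cross-over design for this study". With parallel arms, between-subject variation sets the width of the 90% CI that is compared with 0.8 to 1.25. If weight affects exposure after a fixed dose, a measurable part of that variation is left in the error term.

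The reserve over 90% power is small, and the CV behind it is an approximate figure from interim data of another study at 300 mg. A baseline covariate is a cheap way to add reserve, but it should be chosen before data are seen. The study is open label, so choosing a covariate for the primary model afterwards would carry little weight.

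**Working it through.** **Inputs from Protocol 10.1 and SAP section 7.** There are 80 subjects per arm, CV is about 35%, the limits are 0.8 to 1.25, and the CI is 90%. The power statement is made "assuming the true ratio is 0.95 and 12.5% of subjects will not contribute to the endpoint".

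**Reproducing the stated power.**
- Evaluable per arm: 80 × (1 − 0.125) = 70.
- Log-scale SD: √ln(1 + 0.35²) = 0.340.
- Standard error of the log ratio: 0.340 × √(2/70) = 0.0575.
- Power is that of two one-sided 5% tests, integrated over the chi-square distribution of the residual variance. Residual df are 140 − 1 − 1 − 2 − (sites − 1). The number of sites is not given. Assuming 3 gives 134 df, and using 1 or 6 changes power by at most about 0.02 points.
- Result: 90.7% at 70 per arm, 90.4% at 69, 90.0% at 68 and 89.6% at 67. The plan's figure is confirmed.

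**Adding weight.** Let R² be the share of residual log-scale variance that weight explains. The residual SD becomes 0.340 × √(1 − R²) and one more df is spent. Chance imbalance in weight between arms multiplies the variance of the device contrast by 1/(1 − b), with b ~ Beta(1/2, df/2); power is averaged over b. The documents give no R², so the range is assumed. The second column turns R² into the size of effect it implies: the slope of log exposure on log weight times SD(log weight), which equals √R² × 0.340.

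| Assumed R² | Slope × SD(log weight) | Power at 70 per arm | CI width multiplier (log scale) | Evaluable per arm for 90.7% power |
|---|---|---|---|---|
| 0 | 0 | 90.5% | 1.004 | – |
| 0.03 | 0.06 | 91.3% | 0.99 | 69 |
| 0.05 | 0.08 | 91.8% | 0.98 | 68 (67 is 0.02 points short) |
| 0.1 | 0.11 | 93.0% | 0.95 | 64 |
| 0.2 | 0.15 | 95.2% | 0.90 | 57 |
| 0.3 | 0.19 | 97.1% | 0.84 | 50 |

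Break-even with the unadjusted 90.7% is at R² of about 0.008.

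**Checks.** Simulation of 20,000 trials per R², with 3 sites not balanced by arm, gave adjusted power of 90.4, 91.2, 91.4, 93.0, 94.9 and 96.8% for the six rows. A separate simulation (R² 0.1 to 0.3, site omitted) at a true ratio of 0.80 gave type I error of 5.0 to 5.1% without weight and 4.9 to 5.2% with it. Both models are therefore valid. Ignoring chance imbalance raises the adjusted power at R² of 0.05 to 0.3 by only 0.1 to 0.2 points.

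**Sensitivity to the CV (assumed values, 70 per arm).**

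| CV | Unadjusted | R² 0.05 | R² 0.1 |
|---|---|---|---|
| 33% | 93.3% | 94.2% | 95.1% |
| 37% | 87.9% | 89.1% | 90.6% |
| 40% | 83.1% | 84.6% | 86.4% |

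**The case against.** The strongest reply is that nothing here is broken. The model is the same in both documents, it contains injection site (the stratification factor), and it meets its power. A further covariate is a matter of preference, and its benefit rests on a quantity the documents do not report. A wide BMI range and a fixed dose show that weight varies, not that exposure varies with it. At R² of 0.03 to 0.05 the gain is only 0.6 to 1.1 points.

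The reserve may also be larger than it looks. Subjects with insufficient PK samples may be replaced, though whether beyond 160 is not stated. With no loss at all (80 per arm), power is 93.8%. The CV could be below 35% as easily as above it. If the 35% is a raw CV, the two site factors may already reduce it.

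All of this stands as to the size of the gain. It does not remove the asymmetry: the loss is capped at about 0.2 points, while the gain is several points if weight explains 10% or more of the variance. The general allowances for exploratory and supplementary analyses (Protocol 10.3, SAP section 3) let weight be examined later, but they do not prespecify it in the primary model. Using weight only in a sensitivity analysis would disturb the plan less, but would add no power to the primary comparison.

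Two sets of results could disagree about the limits. Naming one model as primary in advance settles which governs.

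**Conclusion.** The point holds as an optional gain in efficiency, not as a defect. The weight term is absent, the measurement is already scheduled, and the planned analysis remains unbiased, valid and powered at 90.7% under its own assumptions. Adjustment changes power by −0.2 points at R² = 0, +1.1 at 0.05, +2.3 at 0.1 and +4.5 at 0.2. These figures assume 70 evaluable per arm, a true ratio of 0.95, and that the 35% is the residual CV before weight enters. The omission and the conditional arithmetic are certain. Whether weight explains a useful share of the variance cannot be known from the documents.

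**What to change.** Before first dosing, which is when SAP section 3 requires sign-off:

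- Add log(Day 1 predose weight) to the models for log Cmax, log AUC(0-∞) and log AUC(0-tlast). In the code, append a continuous variable such as `log_wt` to the MODEL statement and leave it out of CLASS.
- If the Day 1 weight is missing, use the screening weight.
- Name this the primary model and keep the three-term ANOVA as supportive, stating that the primary model governs the comparison with 0.8 to 1.25.
- Record the departure from the protocol model in SAP section 11, which now reads "There were no changes from the protocol specified statistical analyses". SAP section 3 already provides that the SAP supersedes the protocol's statistical section and that substantial differences are identified.

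The cost is one model term, a few lines in SAP 9.3.2, an entry in section 11 and a second set of results to report. No new data or visits are needed, and the statistical price is about 0.2 points of power if weight explains nothing.

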5.1. Overall Design

This will be a Phase 1, multi-center, open-label, 2-arm (PFS, autoinjector), randomized, parallel group study where a single dose of 240 mg LY2951742 will be administered to healthy subjects.

[figure not shown]
Screening will occur up to 45 days prior to dosing with LY2951742.

Subjects will be admitted to the clinical research unit (CRU) on Day -1. Subjects will be randomized in a 1:1 ratio to 240 mg LY2951742 as a PFS (reference) or 240 mg LY2951742 as an autoinjector (test). All doses will be administered in the morning of Day 1 as two 1-mL subcutaneous injections of 120 mg/mL solution of LY2951742. Subjects will be stratified to receive injections in the upper arm, abdomen, or thigh in each arm of the study, with similar numbers of subjects for each site of injection.

Subjects will remain resident at the CRU until the procedures scheduled at 24 hours postdose have been completed on Day 2, or longer at the discretion of the investigator. All subsequent procedures will be performed on an outpatient basis over a period of approximately 20 weeks (5 half-lives of LY2951742) after study drug administration, including an end-of-study visit (Day 141).

Blood samples will be collected up to 20 weeks postdose to determine serum concentrations of LY2951742 for PK assessments and plasma concentrations of CGRP for PD assessments, and to determine the potential occurrence of ADA and neutralizing antibodies. Safety and tolerability will be assessed by recording of TEAEs, ISR, vital signs (blood pressure and pulse rate), 12-lead electrocardiograms (ECGs), physical examination, clinical chemistry, hematology, and urinalysis.

Figure CGAQ.1 illustrates the study design.

Abbreviations: CRU = clinical research unit; D = day; PFS = prefilled syringe; SC = subcutaneous.

Figure CGAQ.1. Illustration of study design for Protocol I5Q-MC-CGAQ.

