7.2. Method of Treatment Assignment

Subjects will be randomized in a 1:1 ratio to treatment with LY2951742 administered as a PFS or autoinjector. Assignment to the injection device (PFS or autoinjector) and injection site (arm, abdomen, or thigh) will be determined by a computer-generated randomization schedule provided to each site.

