## 5. STUDY DESIGN

[figure not shown]
This will be a Phase 1, multi-center, open-label, 2-arm (PFS, AI), randomized, parallel group study where a single dose of 240 mg LY2951742 will be administered to healthy subjects.

Screening will occur up to 45 days prior to dosing with LY2951742.

Subjects will be admitted to the clinical research unit (CRU) on Day -1. Subjects will be randomized in a 1:1 ratio to 240 mg LY2951742 as a PFS (reference) or 240 mg LY2951742 as an AI (test). All doses will be administered in the morning of Day 1 as two 1-mL subcutaneous injections of 120 mg/mL solution of LY2951742. Subjects will be stratified to receive injections in the upper arm, abdomen, or thigh in each arm of the study, with similar numbers of subjects for each site of injection.

Subjects will remain resident at the CRU until the procedures scheduled at 24 hours postdose have been completed on Day 2, or longer at the discretion of the investigator. All subsequent procedures will be performed on an outpatient basis over a period of approximately 20 weeks (5 half-lives of LY2951742) after study drug administration, including an end-of-study visit (Day 141).

Figure 1.

Abbreviations: CRU = clinical research unit; D = day; PFS = prefilled syringe; SC = subcutaneous

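### The tmax comparisons ignore injection site, although device is balanced within it by design; if tmax location differs by site, the test is conservative (low priority)

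*SAP*

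**What the plan says.** On design, SAP section 5 states "Subjects will be randomized in a 1:1 ratio" to the two devices, and "Subjects will be stratified to receive injections in the upper arm, abdomen, or thigh in each arm of the study". Protocol 5.1 adds "with similar numbers of subjects for each site of injection". Under Protocol 7.2, device and injection site are assigned together: both "will be determined by a computer-generated randomization schedule provided to each site". Device is therefore balanced within injection site on purpose.

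On analysis, SAP 9.3.2 uses that structure for AUC and Cmax: "The model will include fixed effects for injection device (PFS [reference] or AI [test]), investigative site, and injection site". For tmax the same section says only that it "will be analyzed using a Wilcoxon rank-sum test", and then "An estimate of the median difference and 90% CI will be calculated". It names no method for that interval, and the next sentence is an unfilled template line, "Insert stats methodology here". Protocol 10.3.2.2 has the same tmax test. Protocol 10.3.3.2 and SAP 9.4.2 apply it to CGRP tmax, again without stratification, while the CGRP ANOVAs do include injection site.

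On status, Protocol section 4 does not list tmax as a primary or secondary endpoint, and Protocol 10.3.2.1 places it among the other parameters that may be reported.

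**The concern.** When an allocation balances device within a factor, differences between levels of that factor cannot bias the device comparison, and they add almost nothing to its sampling variance. A rank-sum test on pooled data does not know this. Its null variance is computed as if all 140 or so tmax values could have fallen in either arm, so any between-site spread counts as noise. The test then rejects less often than its nominal level, and a shift interval obtained by inverting it is wider than it needs to be.

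At stake is the one planned direct comparison of the timing of absorption, in a study meant to bridge the Phase 3 syringe to the planned commercial autoinjector. A reader who takes a non-significant tmax result as reassurance would be relying on a test that may have less power than the design allows. The documents treat injection site as relevant: it is balanced, modelled for AUC and Cmax, and used to break down the parameter summaries in SAP 9.3.1. They give no reason for leaving it out of the tmax test.

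**Working it through.** **Inputs from the documents.** 160 enrolled, 80 per arm, 12.5% not contributing (SAP section 7); three injection sites in similar numbers in each arm (SAP section 5); 90% CI for the tmax difference (SAP 9.3.2), so a two-sided 10% level; sampling days from the Protocol's Schedule of Activities; tmax of 7 to 14 days overall in Study CGAA (Protocol 3.2).

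**Assumptions, because the documents give no tmax by injection site and no tmax variability.** Log-normal tmax with within-site log SD σ = 0.45; 23, 23 and 24 subjects per site in each arm; a range of site spreads, expressed as the ratio R of the highest to the lowest site median.

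**Step 1: the plan's own figure.** Evaluable subjects: 160 × 0.875 = 140, or 70 per arm. With CV 35%, the log SD is √ln(1 + 0.35²) = 0.340. Two one-sided 5% tests with limits 0.8 to 1.25 and true ratio 0.95 give 90.7% power, so the stated 90% reproduces. It concerns AUC and Cmax; the plan states no operating figure for tmax. Step 1 only fixes 70 per arm for what follows.

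**Step 2: approximate size of the effect.** For three equally spaced log medians with range ln R, the between-site variance is τ² = (ln R)²/6. The true variance of the pooled rank-sum statistic, relative to the one it assumes, is then about v = σ²/(σ² + τ²), and the true error is about 2[1 − Φ(1.645/√v)]. For R = 2: τ² = 0.693²/6 = 0.0801; v = 0.2025/0.2826 = 0.717; 1.645/√0.717 = 1.943; error 5.2%.

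For power, take the stratified power for a 1.2-fold device shift as 73.5% (middle of the simulated 73-74%). That corresponds to a standardised effect of 1.645 + 0.628 = 2.273, and unstratified power is about Φ(2.273 − 1.645/√v). For R = 2: Φ(0.330) = 63%.

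**Step 3: simulation.** tmax rounded to the sampling grid, tie-corrected tests, unstratified results beside the Step 2 approximation:

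| Site spread R | v | Error, formula | Error, simulated | Power at 1.2-fold, formula | Power at 1.2-fold, simulated |
|---|---|---|---|---|---|
| 1.25 | 0.961 | 9.3% | about 9.8% | 72% | about 73% |
| 1.5 | 0.881 | 8.0% | 7.8% | 70% | about 69% |
| 2 | 0.717 | 5.2% | about 5% | 63% | about 63% |
| 3 | 0.502 | 2.0% | about 2% | 48% | about 47% |

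The van Elteren test stays near 10% error and 73-74% power throughout. With no site difference, both tests have about 10% error and 74% power. At R = 1.25 the formula and the simulation differ by half a point; either way the loss is negligible. For a larger device shift of 1.3-fold, power is 94.8% against 95.3% stratified at R = 1.25, 94.1% against 95.2% at 1.5, 90% against 95% at two-fold and 81% against 95% at three-fold.

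**Step 4: sensitivity.**
- Log SD 0.5 instead of 0.45: unstratified error 9.5-9.8%, 8.3-8.5%, 6.1% and 2.5-2.7% at the same four spreads.
- Simple randomisation without balance within injection site: error stays at 9.7-10.3%, so the loss arises because the balance is ignored.
- Day scale, SD 3.5 days, site means 1.5, 3, 5 and 7 days apart: error 9.4%, 8.2%, 5.6% and 3.0%. With 20 of 160 lost at random: 9.6%, 8.7%, 6.1% and 4.0%.
- Sites differing only in spread and not in location: error 10.0%, no effect.
- If the 90% CI is a Hodges-Lehmann interval (day scale, same four separations): coverage about 90%, 92%, 94% and 96%, with mean width rising from 2.01 days at zero separation to 2.64 days at 7.

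**The case against.** The strongest reply is that a prespecified rank-sum test is valid, does not inflate type I error, and is used on a parameter that decides nothing. tmax has no margin, no decision rule and no power claim. Cmax, a primary endpoint that also reflects absorption rate, is already analysed with injection site in the model. SAP 9.3.1 and 9.4.1 promise parameter summaries by treatment and injection-site location, so a site effect on tmax would be visible. Moreover, the documents show no site effect. Up to a 1.5-fold spread the cost for a 1.3-fold device shift is about one point of power, and two- and three-fold spreads centred on 7 days put some site medians below the 7 to 14 days reported in Protocol 3.2. All of this stands, and it is why the priority is low.

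The ANOVA also adjusts for investigative site, which a test stratified by injection site alone does not. That stands too: the SAP should say why it is left out. The documents do not give the number of investigative sites, so whether crossing the two factors would leave usable strata cannot be judged.

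A reader might take the template line in SAP 9.3.2 to mean that no tmax method is specified. It does not: the two sentences before it name the test, the estimate and the confidence level. Only the interval method is missing. The line is an editorial remnant and lends no support to the case for stratifying.

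**Conclusion.** The point holds in conditional form. The tmax tests leave out a factor within which device is balanced; if tmax location differs by injection site, they are conservative. Under the assumptions above, the effect is negligible at a 1.25-fold site spread, small at 1.5-fold (error 7.8%, about four to five points of power for a 1.2-fold shift) and material from two-fold upwards (error 5% or less, power down by about ten points or more).

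Three stronger readings are not supported. First, a reader might infer that the planned tmax interval is too wide. That needs a location difference between sites, for which the documents give no data, and an interval obtained by inverting the rank-sum test, which the SAP does not specify. Second, a reader might infer that any site difference has this effect; a difference in spread alone does not. Third, a reader might infer that the bridging conclusion is weakened. It rests on AUC and Cmax, whose models already contain injection site.

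What remains is a small efficiency gain that costs no power when sites do not differ.

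**What to change.** In SAP 9.3.2, delete the template line and replace the rank-sum test with a van Elteren test stratified by injection site (arm, abdomen, thigh). Name the estimate: a stratum-aligned Hodges-Lehmann shift, autoinjector minus PFS, with its 90% CI. State in one sentence why investigative site is not also a stratum. Make the same change for CGRP tmax in SAP 9.4.2, and record both in SAP section 11 as departures from the unstratified test in Protocol 10.3.2.2 and 10.3.3.2.

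The cost is a few lines of SAP text and a short extra program: the van Elteren test does not itself produce the aligned interval, which needs its own specification. No change to the design, data collection or sample size is involved.
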